Protocol Title: Functional connectivity as a biomarker of rTMS

Abbreviated Title: rTMS / functional connectivity

Protocol Number: 17-N-0055

Date of This Submission/Version: November 13, 2019/ Version H

Principal Investigator: [name]
Behavioral Neurology Unit
National Institute of Neurological Disorders and Stroke
[name]
[name]
[name]
[contact]
E-mail: [contact]

Human Research Protections Program Investigator and Staff Training:

For this protocol, the following “Just in time” human subjects protection training courses are required for investigators and staff:

- CITI GCP modules
- Unanticipated Problems and Reporting Requirements in Biomedical Research

Total requested accrual: 101

101 Healthy Volunteers

Project Uses Ionizing Radiation: No Yes

IND/IDE No Yes

Durable Power of Attorney No Yes

Multi-institutional Project No Yes

Data and Safety Monitoring Board No Yes

Technology Transfer Agreement No Yes

Samples are being stored No Yes

Flesch-Kincaid reading level of consent form: 8 (for HVs)

PRÉCIS

Objective: To use resting state functional connectivity (FC) as a biomarker of synaptic modulation by repetitive transcranial magnetic stimulation (rTMS) in paradigms intended to improve memory and learning. Ancillary outcomes include the effects of rTMS on the interaction between the explicit implicit memory systems.

Study population: Healthy adult volunteers

Design: The study contains two experiments. Experiment 1 is designed to establish the number of rTMS sessions required to produce a meaningful change in resting parieto-hippocampal FC in healthy subjects. Experiment 2 will replicate a prior experiment which used rTMS to enhance the explicit memory system in healthy subjects, and look for potential effects on the implicit system. This intervention will be contrasted with a negative control condition (vertex stimulation) in a between-groups design.

Outcome measures: The primary outcome measures are the change in FC produced by serially applied rTMS and improvement in explicit memory. We will explore whether enhancement of the explicit system has effects on resting state connectivity in the implicit system and whether white matter integrity predicts changes in FC in healthy subjects.

Table of Contents

List of Abbreviations	8
1. Introduction and Background	9
a. Background	9
b. Functional Connectivity as a stable biomarker	10
c. Dose finding using continual reassessment method (CRM)	11

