Learning and memory rely on two primary systems, an “implicit” system, which supports learning by practice and experience under feedback conditions and an “explicit” system, which supports the storage of conscious knowledge. Implicit memory relies on parallel cortical-basal ganglia loops, which operate under the modulatory influence of catecholaminergic projections from the midbrain. The explicit system resides in the hippocampus, amygdala, and related areas. These systems may be in some degree of competition (Ashby & Maddox, 2011; Ashby & Maddox, 2005; Packard & Knowlton, 2002; Poldrack & Packard, 2003). As noted above, Wang et al. (2014) targeted the hippocampus and used a test of the explicit memory system as a behavioral outcome.

In our second experiment, we will use rTMS to increase connectivity in pathways an explicit memory task. We will target the parieto-hippocampal pathway, as Wang et al. (2014) did. We hypothesize that FC will increase only in the targeted pathways and that there will be a parallel dissociation in the effects on implicit and explicit memory. This will confirm our overall hypothesis that pathways involved in specific cognitive processes can be targeted selectively. We will also include a negative control condition (vertex stimulation) to control for sensory and other nonspecific effects of rTMS.

e. Measuring mentation during resting-state scans.

Recent work has revealed that mentation patterns during resting state scanning correlates with functional connectivity measurements (Gregory et al., 2016). Because differences in mentation between participants are difficult to control and could potentially explain our results, we have decided to include a measure of mentation (the Amsterdam Resting-State Questionnaire) as an exploratory measure to our protocol (see Appendix F).

f. Targeting the implicit learning system

The original version of this protocol included a dorsolateral prefrontal stimulation arm, the purpose of which was to attempt to enhance connectivity in the implicit learning system via fronto-striatal pathways. However, this proved infeasible, due to subject discomfort. This protocol now concentrates on the effects of parietal stimulation on FC and implicit and explicit learning.

g. Enhancing hippocampal network FC in TBI patients

We originally planned to pilot the paradigm for explicit memory system enhancement in amnestic TBI patients. This plan has been dropped because of time and resource constraints.

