2. Study Objectives and hypotheses

The overall objective of this study is to determine whether functional connectivity can be used as a biomarker of rTMS synaptic modulation. The experiments outlined in this protocol will not be used to demonstrate the clinical effects of rTMS.

a. Aims

Experiment 1

Specific Aim 1: To determine the number of rTMS sessions required to produce a substantial change in FC between the parietal cortex and hippocampus in healthy subjects.

Experiment 2

Specific Aim 2: To determine whether rTMS delivered to the parietal cortex increases parietal-hippocampal FC in healthy subjects.

Specific Aim 3: To measure the effect of parietal rTMS on AMT and WPT-I, performance.

Specific Aim 4: To evaluate the relationship between fMRI connectivity and AMT and WPT-I outcomes after parietal rTMS in healthy subjects.

b. Hypotheses

i. Primary Hypotheses

Experiment 2: rTMS of the left parietal cortex will increase FC between the left parietal cortex and the hippocampus compared to rTMS of the vertex. rTMS of the left parietal cortex will significantly increase explicit memory compared to rTMS of the vertex.

ii. Secondary hypotheses:

Experiment 2: rTMS of the left parietal cortex will decrease FC between the left caudate (head) and parietal cortex compared to rTMS of the vertex. rTMS of the left parietal cortex will significantly decrease implicit memory compared to rTMS of the vertex.

3. Subjects

a. Description of study populations

We will study 50 healthy individuals (Experiment 1: 18; Experiment 2: 32). We are requesting up to 101 healthy volunteers as the accrual ceiling to account for dropouts and screening failures.

b. Inclusion criteria

Healthy individuals in Experiments 1 and 2.

- Age 18-50 (inclusive)
- English speaking and writing

c. Exclusion criteria

- Any current major neurological or psychiatric disorder such as (but not limited to) stroke, Parkinson disease, Alzheimer disease, schizophrenia or major depression
- History of seizure
- Medications acting on the central nervous system
- Ferromagnetic metal in the cranial cavity or eye, implanted neural stimulator, cochlear implant, or ocular foreign body
- Implanted cardiac pacemaker or auto-defibrillator or pump
- Non-removable body piercing
- Claustrophobia
- Inability to lie supine for 1 hour
- Pregnancy, nursing, or plans to become pregnant during the study.
- Members of the NINDS Behavioral Neurology Unit (BNU)
- For Experiment 2: Participation in Experiment 1

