To reduce the risks of hearing loss associated with rTMS, all subjects will be fitted with hearing protection.

8. Subject Safety Monitoring

For healthy subjects, a credentialed physician or nurse practitioner will be on site for all rTMS administration and immediately available. This is the standard of care in community and academic clinical and experimental rTMS centers, nationwide. Study staff will be trained in rTMS administration, rTMS safety, and the measurement of the motor evoked potential threshold and will have performed 10 measurements under supervision. Study staff will monitor individuals during participation and participants will be encouraged to tell experimenters of any discomfort. Any subject exhibiting distress or who wishes to stop the experiment for any reason will be allowed to stop. Participants may withdraw at any time. Data of those participants that have completed at least the first session of either Experiment 1-2 (i.e. both MRI scan and behavioral assessment) will be kept and analyzed. A researcher may end experimentation for the following reasons:

- 1) Abnormal response to rTMS including the occurrence of a seizure, loss of consciousness, or excessive pain or headache produced by rTMS.
- 2) Withdrawal of consent and/or decision to terminate.
- 3) Excessive frustration exhibited by participants on behavioral tasks.
- 4) Decision by legal proxy or patient guardian to terminate participation.
- 5) Subjects withdrawn due to high motor thresholds above the maximum capacity of the stimulator
- 6) Subjects withdrawn due to discomfort of TMS

9. Outcome Measures

a. Primary outcome measures

- Pre-to-post rTMS difference in FC between the left parietal cortex and the left hippocampus (Experiments 1-2) in healthy subjects (Experiments 1 and 2).
- Pre-to-post rTMS difference in AMT scores in healthy subjects (Experiment 2).

b. Secondary outcome measures

- Pre-to-post rTMS difference in WPT-I scores after rTMS in healthy subjects (Experiment 2).

c. Exploratory outcome measures

- Correlations between memory performance and white matter integrity (Experiment 2).

10. Statistical Analysis

a. Analysis of data/study outcomes

i. Experiment 1

Specific Aim 1: To determine the number of rTMS sessions required to produce a substantial change in FC between the parietal cortex and hippocampus in healthy subjects.

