The following aims will be investigated using the optimal sessions determined in Specific Aim 1.

ii. Experiment 2

Specific Aim 2 (Primary Aim 1): To determine whether rTMS delivered to the parietal cortex increases parietal-hippocampal FC in healthy subjects.

For each healthy subject, the Pearson correlation coefficients (r) between time courses of BOLD activity in the parietal and hippocampal areas will be calculated to determine the functional connectivity before and after rTMS stimulation. They will be Fisher-transformed to normalize r values. *We will call this the z scores.* The change in the z scores from pre- to post- stimulation will be assessed using the one-tailed, paired *t* test.

Specific Aim 3: To measure the effects of parietal rTMS on AMT and WPT-I.

First, the change in the AMT scores from pre- to post- stimulation will be calculated. Then, the two sample *t*-tests will be used to compare the changes in the AMT scores between the parietal and the sham groups. Additionally, we will consider using the Wilcoxon rank sum tests when the changes in the AMT scores are not normally distributed in each group.

Next, we will perform a similar analysis for WPT-I scores.

Specific Aim 4: To evaluate the relationship between fMRI connectivity and AMT and WPT-I outcomes in the parietal group in healthy subjects.

For each subject, the Pearson correlation coefficients (r) between time courses of the parietal and hippocampal regions will be calculated to determine the functional connectivity before and after rTMS stimulation. Then, the changes of the z scores (Fisher transformed r values) from pre- to post- simulation will be calculated. Similarly, the changes in AMT scores from pre- to post-simulation will be computed. The linear

regression models will be used to examine the relationship between the change in functional connectivity and the change in AMT scores.

Next, we will repeat a similar analysis using WPT-I scores.

b. Power analysis

Experiment 1: The maximum number of healthy subjects for Experiment 1 is set at 15.

Experiment 2: We propose to recruit 32 healthy participants (16 subjects in each of the parietal and control groups) to participate in Experiment 2.

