We based our sample size estimate on the behavioral results from the study we are replicating (Wang et al., 2014). In Wang et al. (2014), the effect size of the memory increases caused by PPC stimulation, compared to sham stimulation, was 0.75 (Cohen's d). This was achieved using a within-subjects design. Using this effect size, to achieve a β of 0.70 using the between subjects design described in this protocol (Experiment 2), 16 participants are required.

Sixteen subjects per group also achieves sufficient power to detect FC changes. Wang et al. indicate that the mean difference in FC from post to pre stimulation in retrosplenial region was 0.1018 and its standard deviation was 0.09296. Based on their data, we assume that the mean change will be between 0.1008 and 0.1028. We also assumed its standard deviation (SD) will be between 0.085 and 0.10. A one-tailed, paired t-test was used at a significance level of 0.05. Computations were carried out using PASS (Hinze J. [2008] PASS, NCSS, LLC, Kaysville, Utah).

The following table shows estimates of power to address Primary Aim 1 given ten subjects per treatment group.

Mean of paired difference	Estimated standard deviation of the difference	Power
0.1008	0.085	0.96440
0.1018	0.085	0.96698
0.1028	0.085	0.96940
0.1008	0.093	0.93446
0.1018	0.093	0.93833

0.1028	0.093	0.94202
0.1008	0.100	0.90159
0.1018	0.100	0.90651
0.1028	0.100	0.91125

Table 1. Estimated power for primary aim 1 (N=10 in parietal group)

A sample size of ten subjects per group achieves 93.8% power to detect a mean of paired differences of 0.1018 with an estimated standard deviation of differences of 0.093 and with a significance level of 5% using a one-sided paired t-test. Under other scenarios, the estimated powers were greater than 90%.

Assuming a 50% dropout rate, we anticipate enrolling up to 101 healthy subjects (33 for Experiment 1; 64 for Experiment 2).

11. Human Subjects Protection

a. Subject selection

We will recruit healthy participants through referrals from the NIH Clinical Research Volunteer program or through self-referrals to the protocol. We will work to ensure equitable selection.

b. Justification for exclusion of subjects

i. Justification for exclusion of children

Children will not be included. The study is predicated on the work of Wang et al. (2014) who studied participants over the age of 18. Therefore, in order to replicate this result, we will recruit a sample of the same age.

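### The primary connectivity hypothesis is parietal versus vertex, but the only planned test of connectivity change in Experiment 2 is a one-tailed paired pre-post t test with no vertex comparison

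*Combined protocol and SAP*

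**What the plan says.** The primary hypothesis in section 2.b.i is that "rTMS of the left parietal cortex will increase FC between the left parietal cortex and the hippocampus compared to rTMS of the vertex". The précis describes the design in the same terms: "This intervention will be contrasted with a negative control condition (vertex stimulation) in a between-groups design". Section 1.d gives the reason for the second arm: "We will also include a negative control condition (vertex stimulation) to control for sensory and other nonspecific effects of rTMS".

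The analysis for Specific Aim 2 (Primary Aim 1), in section 10.a.ii, computes Fisher-transformed correlations before and after stimulation. It then says: "The change in the z scores from pre- to post- stimulation will be assessed using the one-tailed, paired" *t* test. It names no group and no comparison.

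The next aim in the same section is handled differently. For the associative memory task (AMT), two-sample *t* tests "will be used to compare the changes in the AMT scores between the parietal and the sham groups", and the implicit task (WPT-I) is to be analysed in a similar way.

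The power section (10.b) matches the paired test: "A one-tailed, paired t-test was used at a significance level of 0.05". Table 1 is labelled as 10 subjects in the parietal group, although the planned size is 16 per group.

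**The concern.** The hypothesis concerns a difference between two stimulation sites, while the test concerns change over time. Half of the 32 subjects in Experiment 2 are assigned to vertex stimulation so that nonspecific effects can be removed, yet the stated primary FC test makes no use of them as a comparator.

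Anything that moves FC between the first and last scan counts towards success if it is upward, or hides a real effect if it is downward. Examples are scan order, familiarity with the scanner, arousal, and a general effect of receiving rTMS. One of the trial's two primary hypotheses would then be called supported or not by a test that does not examine it.

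There is also a conditional problem. Section 4.d.iii takes as the parietal target the region with the greatest hippocampal connectivity on the baseline scan. If the outcome is read at that target, the pre value is selected to be high, and regression to the mean pulls the one-arm change downward. Section 10 does not say where FC is read, so this bias is possible but not certain.

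**Working it through.** **Inputs from section 10.b**
- Mean change 0.1018, range 0.1008 to 0.1028.
- SD of change 0.093, range 0.085 to 0.10.
- One-sided alpha 0.05.
- Table 1 uses n = 10; the planned size is 16 per group.

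**Assumptions not in the documents**
- The vertex group's SD of change equals the parietal SD.
- The vertex mean change, or any shift common to both groups, is varied from 0 to 0.05.

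**Step 1. Reproduce the plan's figure.** One-sided paired *t* test: df = n − 1, noncentrality = (mean/SD) × √n.
- n = 10: (0.1018/0.093) × √10 = 3.46, critical value 1.833, power 0.93833. This is the plan's figure. All nine rows of Table 1 reproduce to five decimals, so its power is for a within-group test with no control arm.
- n = 16: (0.1018/0.093) × 4 = 4.38, critical value 1.753, power 99.4%.

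**Step 2. How often the planned test is significant when site has no effect.** Let the same shift occur in both groups, so the true parietal-minus-vertex difference is zero. For 16 parietal subjects, noncentrality = (shift/0.093) × 4.

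| Shared shift (assumed) | Noncentrality | Paired test significant | Two-sample test significant |
|---|---|---|---|
| 0 | 0 | 5.0% | 5% |
| 0.01 | 0.43 | 10.9% | 5% |
| 0.02 | 0.86 | 20.5% | 5% |
| 0.028 | 1.20 | 31.0% | 5% |
| 0.03 | 1.29 | 34.0% | 5% |
| 0.04 | 1.72 | 49.9% | 5% |
| 0.05 | 2.15 | 65.8% | 5% |

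The value 0.028 is included because section 10.a.i uses it as the cut-point for an effective change.

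**Step 3. Power of the test that matches the hypothesis.** Two-sample *t* test on change scores, 16 per group: df = 30, noncentrality = ((0.1018 − vertex change)/0.093) × √(16/2).

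| Vertex change (assumed) | Noncentrality | One-sided power | Two-sided power |
|---|---|---|---|
| 0 | 3.10 | 91.6% | 85.0% |
| 0.01 | 2.79 | 86.1% | 77.1% |
| 0.02 | 2.49 | 78.4% | 67.3% |
| 0.03 | 2.18 | 68.8% | 56.1% |
| 0.04 | 1.88 | 57.6% | 44.4% |
| 0.05 | 1.58 | 45.8% | 33.2% |

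With vertex change 0, the plan's nine combinations of mean and SD give 87.3% to 95.5% one-sided and 78.8% to 91.1% two-sided.

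**Step 4. Look for the comparison elsewhere.** Two other analyses in section 10 use FC. The Experiment 1 dose-finding has no vertex arm. The Aim 4 regression relates FC change to memory change within the parietal group. Neither compares FC between groups.

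**The case against.** The paired test does match part of the document. Specific Aim 2 asks whether parietal rTMS increases FC and names no comparator. The outcome in section 9.a is also a change over time: "Pre-to-post rTMS difference in FC between the left parietal cortex and the left hippocampus". But the AMT outcome is worded in the same way and still gets a two-sample test. The outcome definition fixes the variable, and the hypothesis fixes the contrast. A between-groups FC test may have been intended, but none is written, and the power section names the paired test explicitly.

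The shifts in Step 2 have no source in the documents, which argue the other way. Section 1.b defends FC as stable across sessions, and section 4.d.iii reports that off-target stimulation in the replicated study had no significant effect on connectivity. That is fair: the rates are illustrative. Neither statement establishes a zero shift, and guarding against one is the vertex arm's stated purpose.

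The strongest point concerns cost. The 85% figure assumes no vertex change, while the concern is about shared shifts. The planning mean is itself a pre-post change, so it may contain such a shift. It also comes from another region: "the mean difference in FC from post to pre stimulation in retrosplenial region was 0.1018 and its standard deviation was 0.09296". This stands. The 85% is a favourable case and Step 3 shows how it erodes. It calls for an honest power statement and does not rescue the paired test.

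The regression-to-the-mean point is conditional and, being downward, would make a positive paired result conservative. The conclusion does not depend on it.

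**Conclusion.** The concern holds. The planned analysis of Primary Aim 1 does not test the primary FC hypothesis, and its power figure, though arithmetically correct, belongs to a different contrast. The other primary hypothesis, on explicit memory, is not affected because AMT has a between-group test.

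At n = 16 and SD 0.093, the chance of a significant result with no site effect rises from 5% to between 11% and 50% for assumed shared shifts of 0.01 to 0.04. Against the paired test's 99.4% at the same n, the correct comparison has about 85% power two-sided or 92% one-sided. Those two figures rest on the plan's retrosplenial planning values, equal SDs and no vertex change. Because this governs a primary hypothesis, it should be corrected before the FC data are analysed.

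**What to change.** - In section 10.a.ii, make the parietal-versus-vertex difference the primary FC analysis: ANCOVA of post-stimulation Fisher z on group, with baseline z as covariate. A two-sample *t* test on change is the minimum that meets the need. State whether the test is one- or two-sided.
- Compute FC in both groups by one region rule. If FC is read at the individual parietal target, derive that target in vertex subjects from their baseline scans too. Any regression to the mean then affects both arms alike and cancels in the contrast.
- Keep the paired test as descriptive within-group output.
- Replace Table 1 with power for the between-group contrast at 16 per group, over a stated range of vertex changes, and say how far the retrosplenial values apply to the parietal-hippocampal endpoint.
- Add the matching group comparison for the secondary caudate-parietal FC hypothesis, which is also stated against vertex and has no planned test.

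The cost is SAP wording and a less favourable power figure. The comparison needs no new scans, since both groups are scanned before and after stimulation. Whether 16 per group is enough depends on the vertex change the sponsor considers plausible.

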Upon arrival to the screening appointment, written, informed consent will be obtained by an investigator and formal screening will be done according to Appendix B.

Volunteers who have not had a neurological exam from an NINDS provider within the past two years will receive a neurological examination from an NINDS physician or nurse practitioner. This will not replace any exam the participant will receive for purposes of medical care; the exam will be for research purposes only. All women of child-bearing potential will have a urine pregnancy test (not earlier than 24 hours) before each MRI scan.

d. Study procedures

i. Behavioral tasks

Weather Prediction Task (Implicit version; WPT-I) - This is a test of the ability to learn an implicit, stochastic, association by trial and error and recruits a brain network including the dorsolateral prefrontal cortex and the head of the caudate nucleus, primarily in the right hemisphere. In the WPT, participants learn to predict a binary outcome, based on arbitrary stimuli with a hidden statistical link to that outcome. One, two, or three-card combinations of four possible cards are presented on a computer and the subject is asked to predict the “weather;” i.e. whether it will be rainy or fine. After each prediction, the subject receives corrective feedback. Each card is independently associated with one outcome with a fixed probability. For example, the probability of rainy might be 0.2 for squares, 0.4 for diamonds, 0.6 for circles, and 0.8 for triangles. We will use three different versions of the task at the three test sessions (see below). The task has 150 trials, with breaks after every 50 trials and takes approximately 17 minutes.

Associative Memory Task (AMT) – This is a test of the ability to learn and remember explicit associations between unrelated stimuli and involves the hippocampus and related visual processing areas. Participants are shown 20 face-name combinations (study phase) and are instructed to encode as many of these combinations as possible. Memory of the combinations is immediately assessed afterwards (test phase) by showing participants each individual face and asking them to recall the associated word. As with the WPT, we will use three different versions of the task at the three test sessions. The task takes approximately 10 minutes.

ii. MRI

1. MRI Anatomical scanning

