Experiment 2 will use a between-subjects design (see Figure 4) to study healthy volunteers. All participants will have an initial scanning session on the first day of the study where anatomical, resting-state, and DTI images will be collected. This will be followed by 1-5 days of rTMS (20-minutes per day). The number of days of rTMS will be derived from the results of Experiment 1. On the day after the last rTMS session (within 12-36 hours), a final anatomical and resting-state-scan will be collected. Immediately following each resting-state scan, we will administer the ASRQ. All participants will experience the same procedures, with the exception of the location of stimulation. Depending on group assignment, the participant will either receive stimulation to the parietal cortex, or vertex.

Contrary to Experiment 1, Experiment 2 will include behavioral testing at 3 different time points: 1) after the initial scanning session, 2) after the final scanning session, and 3) about a week after the last scanning session. This will include memory testing using the WPT-I and AMT, as well as the cognitive battery described above.

Subjects will be assigned to two groups (parietal and vertex), which will be balanced by age and sex. We will blind volunteers to stimulation type (group assignment) by recruiting participant who are naïve to the study hypothesis. Investigators scoring FC and behavioral data will be kept blind to rTMS assignment.

[figure not shown]

Figure 4. Procedures for Experiment 2. Times are estimates.

viiii. Duration of Study

Participation for healthy participants in Experiments 1 and 2 will be no more than 8 visits.

e. End of Participation

Volunteers will remain under the care of their own providers. No care will be offered to those participating in this protocol, except for any acute care required for adverse events. Findings of clinical significance, e.g., significant pathology on MRI will be shared with participants and any provider whom they designate.

5. Management of Data and Samples

i. Storage

The results of testing will be stored on password-protected computers or backed up on media stored in locked cabinets. Keys to participant identity will be stored in lab notebooks, available only to study investigators. Samples will not be stored under this protocol.

ii. Data and Sample Sharing Plan

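### AMT, a primary outcome, is compared on raw change; if assignment is random, ANCOVA on the baseline already collected is more precise unless the pre-post correlation exceeds about 0.93

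*Combined protocol and SAP*

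**What the plan says.** Section 9.a lists as a primary outcome "Pre-to-post rTMS difference in AMT scores in healthy subjects (Experiment 2"). Section 2.b.i gives the matching primary hypothesis: "rTMS of the left parietal cortex will significantly increase explicit memory compared to rTMS of the vertex".

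Section 10.a.ii, Specific Aim 3, computes each subject's pre-to-post change and states that two-sample t tests "will be used to compare the changes in the AMT scores between the parietal and the sham groups". The group called sham there must be the vertex group, since Experiment 2 has only two groups. A Wilcoxon rank sum test on the same changes is to be considered if they are not normally distributed. The secondary memory outcome follows suit: "Next, we will perform a similar analysis for WPT-I scores".

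Baseline AMT is available. Sections 4.d.iii and 4.d.viii and Appendix C all place memory testing before the first rTMS session. No baseline adjustment of AMT appears anywhere in the document.

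On group formation, section 4.d.viii says only: "Subjects will be assigned to two groups (parietal and vertex), which will be balanced by age and sex". It gives no allocation method. On size, section 10.b takes d = 0.75 from a within-subjects study and says that "to achieve a β of 0.70 using the between subjects design described in this protocol (Experiment 2), 16 participants are required". The 0.70 is evidently meant as power. The sidedness of the AMT test is not stated.

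**The concern.** A t test on change scores is equivalent to adjusting for baseline with the coefficient fixed at 1. With equal pre and post SDs, the coefficient that minimises variance is the pre-post correlation, rho. Fixing it at 1 therefore adds noise unless rho is very high. ANCOVA estimates the coefficient from data the trial already collects.

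This matters because AMT carries a primary between-group hypothesis with 16 subjects per group and a planned power of only about 70%. At that size, precision that can be had without extra subjects or visits is worth taking.

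**Working it through.** **Inputs.** From the documents: 16 per group (section 10.b); d = 0.75 (section 10.b); alpha 0.05 (stated there only for the one-tailed connectivity test). Assumed: random assignment; equal pre and post SDs; rho from 0.3 to 0.9; both sidedness options; both readings of the SD behind d.

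**1. The plan's own figure.** One-sided normal approximation: 0.75 × √(16/2) = 2.121, and 2.121 − 1.645 = 0.476, so power is Φ(0.476) = 0.683, close to the stated 0.70. The exact noncentral t (30 df) gives 0.666 one-sided and 0.537 two-sided. The 0.70 is thus approached only with a one-sided test. Whether 16 per group is enough is a separate sample-size question and not the basis of this point.

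**2. Variance.** With common SD σ and n per group:
- change score: 2σ²(1 − rho) × 2/n
- ANCOVA: σ²(1 − rho²) × 2/n, times an allowance for chance baseline imbalance

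The ratio is (1 + rho)/2 times the allowance. The allowance has expectation 1 + 1/28 = 29/28 (it is 1 + F/30 with F on 1 and 30 df, whose mean is 30/28). Break-even: (1 + rho)/2 × 29/28 = 1, so rho = 56/29 − 1 = 0.93. This step does not involve d.

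**3. Power.** Noncentral t with 29 df for ANCOVA, averaged over chance baseline imbalance. If d is in change-score SDs, the effective d for ANCOVA is 0.75/√((1 + rho)/2), and the planned test has 67% power one-sided and 54% two-sided at every rho. If d is in post-score SDs, the change-score d is 0.75/√(2(1 − rho)), so the planned test's power itself depends on rho.

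| rho | Net variance ratio | Variance cut | ANCOVA power, d on change SD, one-/two-sided | Gain, one-/two-sided (points) | Planned → ANCOVA, d on post SD, one-sided | Gain (points) |
|---|---|---|---|---|---|---|
| 0.3 | 0.65 × 29/28 = 0.673 | 33% | 81/71% | 14.5/16.8 | 54 → 69% | 14.5 |
| 0.5 | 0.75 × 29/28 = 0.777 | 22% | 76/64% | 9.4/10.7 | 67 → 76% | 9.4 |
| 0.7 | 0.85 × 29/28 = 0.880 | 12% | 71/59% | 4.8/5.3 | 85 → 89% | 3.7 |
| 0.8 | 0.90 × 29/28 = 0.932 | 7% | 69/57% | 2.6/2.9 | 95 → 96% | 1.1 |
| 0.9 | 0.95 × 29/28 = 0.984 | 2% | 67/54% | 0.6/0.6 | – | – |

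Gains are taken from unrounded powers. A simulation of 200,000 trials per rho, with d on the change SD, gave one-sided gains of 14.6, 9.5, 4.7, 2.7 and 0.0 points at rho 0.3, 0.5, 0.7, 0.8 and 0.93. As rho approaches 1 on this scale, ANCOVA loses about 1.4 points.

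**4. What the documents say about rho.** They give no value, but section 4.d.i limits it: "Participants are shown 20 face-name combinations (study phase"), and "As with the WPT, we will use three different versions of the task at the three test sessions". Assume 50% mean recall and a true between-subject SD of s items. Sampling 20 items adds variance 5 − 0.05s², so rho cannot exceed s²/(5 + 0.95s²). That cap is 0.45, 0.66, 0.79, 0.87 and 0.92 for s = 2, 3, 4, 5 and 6. Mean recall and s are both assumptions, so this bounds rho without settling it.

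**The case against.** **The planned test is not wrong.** This stands. It is valid under random assignment and tests exactly the outcome defined in section 9.a. A reader might infer that the primary analysis is in error; the documents do not support that. The point concerns a cheap gain in precision.

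**The gain rests on a correlation nobody has stated.** This stands as a limit on size. Simulating AMT as 20 items at 50% recall, with d on the change-score SD and rho at the caps above, the one-sided gains are 10.4, 5.2, 2.3, 0.8 and −0.4 points for s = 2 to 6. Three of those five are under 2.5 points. True rho may lie below its cap, which would raise the gain. The balance is still uneven: up to about 14 points gained over the range examined, against about 1.4 lost at worst.

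**The power figures depend on which SD d refers to.** This stands. Section 10.b does not name the SD. On the post-score SD the planned test already has 85% one-sided and 75% two-sided power at rho 0.7, and the gains at 0.7 and 0.8 shrink to 3.7 and 1.1 points. The variance reductions are unaffected.

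**Randomisation is not stated.** This stands as a precondition. If the groups could differ systematically at baseline, ANCOVA and change scores can estimate different quantities, and the efficiency comparison no longer applies.

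**A bare switch to ANCOVA would drop the existing provision for non-normal data.** This stands, and the fix keeps one. AMT is a bounded 20-item score. In the simulation at 50% recall, ANCOVA's type I error was 0.049 to 0.052 at nominal 0.05, but recall near floor or ceiling was not examined.

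**Conclusion.** The unadjusted comparison of AMT change is valid but less efficient than ANCOVA for rho below about 0.93, given random assignment and equal pre and post SDs. The firm result is the variance reduction of about 33%, 22%, 12%, 7% and 2% at rho 0.3, 0.5, 0.7, 0.8 and 0.9. The power gain is material at low to moderate rho on either scale of d, small by 0.8, and nil near 0.93.

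A reader might infer that ANCOVA restores the planned 70% power. That is not supported. With d on the change-score SD, it reaches 70% one-sided only for rho up to about 0.76, and two-sided only up to about 0.32. With d on the post-score SD, the planned test may already exceed 70%. Nor can 67% be quoted as the power of the planned test without naming the SD and the sidedness.

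The power figures concern AMT alone. The documents give no effect size for WPT-I, where the change is for consistency. The recommendation is worth adopting, with medium confidence because rho, the scale of d and the allocation method are not in the documents.

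**What to change.** In section 10.a.ii, Specific Aim 3, replace the AMT test with wording such as:

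> The primary analysis of AMT will be an ANCOVA of the post-stimulation score (equivalently, the change) on group and baseline score, reporting the adjusted difference with its confidence interval. The two-sample t test on change will be a sensitivity analysis. If residuals are clearly non-normal, a rank-based or permutation version of the adjusted comparison, or the Wilcoxon test on change already planned, will also be reported. WPT-I will be analysed in the same way.

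With baseline in the model, the group coefficient is the same whether the dependent variable is the post score or the change, so the outcome in section 9.a need not be redefined.

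Before outcome data are examined, confirm in section 4.d.viii that assignment is random and state how it is done, and state whether the AMT test is one- or two-sided. It would also help to say in section 10.b which SD the 0.75 refers to.

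The cost is a change of wording and one degree of freedom (29 instead of 30). No subjects, visits or measurements are added.
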